### 3. OBJECTIVES AND ENDPOINTS

Objectives	Endpoints
Primary – Phase 2	

 
To select maximally tolerated dose for use in Phase 3, and to assess the effect of dociparstat on disease progression in participants with severe COVID-19
 
	
 
Incidence of AEs, severe AEs, and SAEs
 
Proportion of participants who are alive and free of invasive mechanical ventilation through Day 28
 

Primary – Phase 3	

 
To assess the effect of dociparstat on disease progression in participants with severe COVID-19
 
	
 
Proportion of participants who are alive and free of invasive mechanical ventilation through Day 28
 

Key Secondary	

 
To assess the effect of dociparstat on mortality
 
	
 
All-cause mortality through Day 28
 

Secondary	

 
To determine additional evidence of a therapeutic effect of dociparstat in participants with severe COVID-19
 
	
 
Time to invasive mechanical ventilation or all-cause mortality
 
Time to all-cause mortality
 
Proportion of participants who are alive, discharged from the hospital, and not using home oxygen at fixed time points (Days 8, 14, and 28)
 
Clinical status assessed by the NIAID ordinal scale at fixed time points (Days 8, 14, and 28)
 
Time to clinical improvement, defined as time to at least a 2-grade improvement from baseline on the NIAID ordinal scale
 
Number of ventilator-free days from baseline through Day 28
 
Time to hospital discharge
 
Time to resolution of fever, defined as temperature <math>\leq 99.0^{\circ}\text{F}</math> (<math>\leq 37.2^{\circ}\text{C}</math>) and no antipyretic use within the preceding 48 hours (participants with baseline fever only)
 
Change from baseline in C-reactive protein level
 
Change from baseline in serum ferritin level
 
Change from baseline in lactate dehydrogenase level
 
Change from baseline in d-dimer level
 
Daily average of prednisone-equivalent corticosteroid dose through Day 28
 

Objectives	Endpoints

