#### **4.4. End of Study Definition**

A participant is considered to have completed the study if he/she has completed the Day 28 follow-up visit.

The end of the study is defined as the date of the last visit of the last participant in the study.

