3. DERIVATIONS AND DEFINITIONS

Kaplan-Meier estimates

Time to xxx (days): Days are calculated as (start date/time – first study drug date/time)/24h). Time will be censored at last individual date/time reported.

Worst-case results in 2 scenarios for missing time-values:

1. Missing time for negative events will be imputed with “00:01”, missing time for censored observations will be imputed with “23:59”.

Negative events are:

- Time to first invasive mechanical ventilation or ECMO
- Time to first invasive mechanical ventilation, ECMO or all-cause mortality
- Time to all-cause mortality

2. Missing time for positive events will be imputed with “23:59”, missing time for censored observations will be imputed with “00:01”.

Positive events are:

- Time to clinical improvement
- Time to hospital discharge

In addition, to avoid bias in the positive events, deaths occurring prior to the positive event being observed will be censored at Day 28.

Ventilator-free days

Ventilator-free days are only counted from baseline through Day 28 or end of study, whichever comes first. They are derived based on the eCRF data collected on the Ventilator/Oxygen/Medical Care Status CRF page, Ventilator-free days are all days where Ventilator/Oxygen/Medical Care Status is not equal “Invasive Mechanical Ventilation or extracorporeal membrane oxygenation (ECMO)”.

Ventilator days are defined as cumulative rounded number of days with Ventilator/Oxygen/Medical Care Status = “Invasive Mechanical Ventilation or extracorporeal membrane oxygenation (ECMO)” divided by 24 h. Missing time for start will be imputed with “00:01”, missing time for stop will be imputed with “23:59”.

Study duration in days is defined as: Date of study completion (or date of early study discontinuation) – date of first study treatment + 1. For subjects randomized but not treated the date of randomization will be used instead of first study treatment date. The maximum study duration is set to 28 days, even if study completion or study discontinuation is after 28 days.

Ventilator-free days are defined as: study duration - number of ventilator days. For subjects who died during the course of the study, the number of ventilator-free days will be defined as 0.

Randomized, but not treated subjects:

The following rules will apply for randomized subjects without receiving study treatment, if not stated otherwise:

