4	xx (xx.x)	xx (xx.x)	xx (xx.x)	xx (xx.x)
5	xx (xx.x)	xx (xx.x)	xx (xx.x)	xx (xx.x)
6	xx (xx.x)	xx (xx.x)	xx (xx.x)	xx (xx.x)
7	xx (xx.x)	xx (xx.x)	xx (xx.x)	xx (xx.x)
8	xx (xx.x)	xx (xx.x)	xx (xx.x)	xx (xx.x)
...				
28	xx (xx.x)	xx (xx.x)	xx (xx.x)	xx (xx.x)
n	xxx	xxx	xxx	xxx
Mean	xx.x	xx.x	xx.x	xx.x
SD	xx.x	xx.x	xx.x	xx.x
Median	xx	xx	xx	xx
Q1, Q3	xx, xx	xx, xx	xx, xx	xx, xx
Min, Max	xx, xx	xx, xx	xx, xx	xx, xx

N = Number of subjects in a specific group; n = Number of subjects with data available; Percentages are based on N; SD: Standard deviation; Q1, Q3: First, third quartile; Min: minimum; Max: maximum.

Ventilator-free days are only counted through the date of early study discontinuation, study completion date or Day 28, whichever comes first. For subjects who die during the course of the study, number of ventilator-free days is defined as 0.

Page X of Y

(Notes for programmer:

Include only the categories of Days (0-28) in the table which are available in the data
)

Table 24: Time to last hospital discharge - ITT Set

	DSTAT 0.25 N=xxx	Cohort 1 PBO N=xxx	DSTAT 0.325 N=xxx	Cohort 2 PBO N=xxx
Number of subjects discharged from hospital, n (%) (a)	xx (xx.x)	xx (xx.x)	xx (xx.x)	xx (xx.x)
Kaplan-Meier estimates (b)				
Number of censored subjects, n (%) (b)	xx (xx.x)	xx (xx.x)	xx (xx.x)	xx (xx.x)
Number of subjects alive and still in hospital	xx (xx.x)	xx (xx.x)	xx (xx.x)	xx (xx.x)
Death	xx (xx.x)	xx (xx.x)	xx (xx.x)	xx (xx.x)
Time to hospital discharge (days) (b)				
25% Quartile (95% CI)	x.x (x.xx, x.xx)	x.x (x.xx, x.xx)	x.x (x.xx, x.xx)	x.x (x.xx, x.xx)
Median (95% CI)	x.x (x.xx, x.xx)	x.x (x.xx, x.xx)	x.x (x.xx, x.xx)	x.x (x.xx, x.xx)
75% Quartile (95% CI)	x.x (x.xx, x.xx)	x.x (x.xx, x.xx)	x.x (x.xx, x.xx)	x.x (x.xx, x.xx)

N = Number of subjects in a specific group; n = Number of subjects with data available; Percentages are based on N;
 (a) Subjects discharged from hospital will be counted as event.

(b) Kaplan-Meier estimates: Subjects discharged from hospital will be counted as event. Subjects who are still in the hospital or died in the hospital will be censored.

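### If study completion is dated at the Day 28 visit, survivors off the ventilator who are seen on Days 25–27 lose 1–3 ventilator-free days through visit timing alone

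*SAP*

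**What the plan says.** The protocol (Section 3) lists as a secondary endpoint "Number of ventilator-free days from baseline through Day 28".

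SAP Section 3 opens its derivation with "Ventilator-free days are only counted from baseline through Day 28 or end of study, whichever comes first". The score is then set by formula: "Ventilator-free days are defined as: study duration - number of ventilator days". The duration definition begins "Study duration in days is defined as: Date of study completion (or date of early study discontinuation" and goes on to subtract the first-treatment date and add 1. An upper limit follows: "The maximum study duration is set to 28 days, even if study completion or study discontinuation is after 28 days". There is no matching rule that brings a shorter duration up to 28. Participants who die score 0.

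The Table 23 footnote repeats the rule: "Ventilator-free days are only counted through the date of early study discontinuation, study completion date or Day 28, whichever comes first".

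On completion, Protocol 4.4 says: "A participant is considered to have completed the study if he/she has completed the Day 28 follow-up visit". The Schedule of Activities (Protocol Table 1) gives that visit a window of 3 days either side and sets Day 1 as the day of first dose.

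**The concern.** Taken together, these rules let a completer's score depend on which day of the permitted window the last visit was held. The dependence runs one way: an early visit removes days, and the cap stops a late visit from adding any. A never-ventilated completer seen on Day 25 gets the same score as one seen on Day 28 after three days on the ventilator, and Table 23 cannot tell them apart.

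This does not match the protocol's through-Day-28 horizon. It also sits badly with SAP Table 18, where early discontinuation disqualifies a participant from the ventilation-free count only if it occurs before Day 25. A never-ventilated Day-25 completer is therefore ventilation-free to Day 28 in Table 18 and three days short in Table 23.

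What is at stake is the reading of one descriptive table. Table 23 gives a day-by-day distribution, mean and median for very small arms, and some of the spread below 28 could be appointment dates rather than ventilation.

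**Working it through.** The documents give no worked score to reproduce, so the check applies the SAP formula across the visit window.

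**Inputs**
- Window for the Day 28 visit: Days 25 to 31 (Protocol Table 1).
- Duration = completion date − first-treatment date + 1. With Day 1 as first dose, this equals the study day of completion (SAP Section 3).
- Cap: 28 days (SAP Section 3).
- Arm sizes: 6 and 6 in Cohort 1, 8 and 4 in Cohort 2 (Protocol 4.1).
- Assumption 1: the completion date is the date of the Day 28 visit. Protocol 4.4 implies this, but the SAP does not state it.
- Assumption 2: ventilation is counted in whole calendar days. The SAP uses hours divided by 24, rounded.

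**Formulas**
- SAP rule: score = min(28, completion day) − ventilator days.
- Fixed horizon: score = 28 − ventilator days through Day 28, with the last status carried forward.

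| Day of the Day 28 visit | 25 | 26 | 27 | 28–31 |
|---|---|---|---|---|
| Never ventilated, SAP rule | 25 | 26 | 27 | 28 |
| Never ventilated, fixed horizon | 28 | 28 | 28 | 28 |
| 6 ventilator days then weaned, SAP rule | 19 | 20 | 21 | 22 |
| 6 ventilator days then weaned, fixed horizon | 22 | 22 | 22 | 22 |
| Days lost under the SAP rule | 3 | 2 | 1 | 0 |

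**Who is not affected**
- Deaths score 0 under both rules.
- A completer ventilated from Day 5 up to a Day-25 visit has 21 ventilator days by then: 25 − 21 = 4 under the SAP rule. Carrying the status to Day 28 gives 24 ventilator days: 28 − 24 = 4. No change.

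**Effect on an arm mean of one Day-25 visit in place of Day 28**
- n = 8: 3/8 = 0.375 days.
- n = 6: 3/6 = 0.5 days.
- n = 4: 3/4 = 0.75 days.

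For scale, one death scored 0 in place of 28 moves the same means by 28/8 = 3.5, 28/6 = 4.7 and 28/4 = 7.0 days, about nine times as much (28/3 = 9.3).

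**Expected loss per completer off the ventilator**
The documents give no distribution of visit dates, so this is a range under assumptions. If a share p is seen evenly over Days 25–27, the expected loss is p × (3 + 2 + 1)/3 = 2p.
- p = 0.10: 0.20 days.
- Visits even over Days 25–31, so p = 3/7: 0.86 days.
- The limits are 0 (every visit on Day 28 or later) and 3 (every visit on Day 25).

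**The case against.** The strongest defence is that the rule is deliberate. Two places in the SAP state it and they agree. The SAP also counts observed time only in its Kaplan-Meier outputs, including the time-to-event part of Table 18, where follow-up ends at the last reported date. A reader might infer that ventilator-free days is the one place where the SAP departs from its own handling of the window. The documents do not support that, because stopping at the end of observation is the SAP's convention for time-based quantities. The comparison still does not justify the formula. Censoring leaves unobserved time neutral, whereas this subtraction treats it as time not free of the ventilator.

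Tables 20 and 21 are a looser precedent than they appear. Their last-status rules are written for participants who discontinue inside the window, and they assign one status at one visit. They do not credit days to completers. They lend a principle that would have to be extended. The Day-25 boundary in Table 18 is the closer parallel, though it governs a yes/no classification rather than a count of days.

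The mechanism also depends on what sites enter as the completion date. The protocol expects follow-up through Day 28, and the case report form is not available to check. If completion is never dated before Day 28, the loss is zero. This part of the objection stands and limits confidence.

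A reader might also infer that the formula can give negative scores, since the ventilator-days sentence ("Ventilator days are defined as cumulative rounded number of days with Ventilator/Oxygen/Medical Care Status") does not repeat the Day-28 limit. The opening sentence and the Table 23 footnote already limit the counting to Day 28, so the matter is one of tidy wording.

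**Conclusion.** The point holds as a minor one, with moderate confidence. If completion is dated at the Day 28 visit, the formula removes 1 to 3 ventilator-free days from surviving completers who are off invasive ventilation and ECMO and are seen on Days 25–27. The loss comes from scheduling and departs from the protocol's horizon.

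It would be easy to read this as a bias in the treatment comparison. The documents give no reason to expect visit dates to differ by arm, so a general downward shift and added noise are all that can be claimed. Nor does it reach any confirmatory result: Protocol 9.4 makes the Cohort 1 and 2 analyses descriptive and gives Phase 3 its own SAP.

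**What to change.** In SAP Section 3:
- For participants alive and followed to Day 25 or later, set the horizon to 28 days and carry the last ventilation status to Day 28. This extends the Day-25 boundary of Table 18 and the in-window last-status principle of Tables 20 and 21.
- Keep the score of 0 for deaths, and keep the observed-days rule for those who discontinue alive before Day 25.
- State in the ventilator-days sentence that counting stops at Day 28.
- Say what date is used for study completion.

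Align the Table 23 footnote with these rules.

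The cost is a few lines of text and no new data. There are two drawbacks. Up to 3 days of unobserved status are credited. The step at Day 25 also grows: a never-ventilated participant who leaves on Day 24 scores 24, while one followed to Day 25 scores 28 instead of 25, so the step is 4 days instead of 1. If the sponsor prefers not to credit unobserved days, the Table 23 footnote should at least say that scores below 28 may reflect visit timing.

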4. CONVENTIONS FOR SUMMARY TABLES AND LISTINGS

At the top of each table/listing/figure, the first three title lines should read:

Chimerix
CMX-DS-004
Post-Cohort 1/2 Lock Analysis - FINAL (Unblinded)

Following those titles, the next title should include the output number and a description of the table/listing content, including the Analysis Set used.

The next line is an optional sub-title with description of a subgroup, if applicable.

Horizontal lines will appear before and after the column heading of the table/listing. Footnotes will be put under the main body of text and each new footnote should start with a new line. Very long footnotes will be presented only on the very first page of the output.

At the bottom of each TFL, the following information should be printed: date of the data base cut off, date and time of the run of the TFL and name of the program.

Data Cut-off date: DDMMYYYY;
Program name: M:\project-sas\chimerix\7015085\biostat\3-cohort\tables\production\xxxxx.sas
Run date: DDMMYYYY HH:MM

Page X of Y

Outputs will be prepared in landscape layout unless otherwise specified. Blank margins of all tables and listings will be a minimum of 1 inch. In general, Courier New 8 point font will be used.

Listings Layout

Listings will contain the data of all subjects except when otherwise specified. The following visit labels will be used (shorthand in parentheses), but data will be sorted by assessment date (including the Unscheduled Visits):

- Screening (SCRN)
- Baseline (D1)
- Day 2 (D2)
- Day 3 (D3)
- Day 4 (D4)
- Day 5 (D5)
- Day 6 (D6)
- Day 7 (D7)
- Day 8 (D8)
- Day 14 (D14)
- Day 28 (D28)
- Early Tx DC (TXDC)
- Unscheduled (UNSCH)

5. TABLE SHELLS

5.1. DMC – TABLE SHELLS

Table 1: Demographics and Baseline Characteristics – Safety Set

	DSTAT 0.25 N=xxx	Cohort 1 PBO N=xxx	DSTAT 0.325 N=xxx	Cohort 2 PBO N=xxx	Total N=xxx
Gender, n (%)					
Male	xxx (xx.x)	xxx (xx.x)	xxx (xx.x)	xxx (xx.x)	xxx (xx.x)
Female	xxx (xx.x)	xxx (xx.x)	xxx (xx.x)	xxx (xx.x)	xxx (xx.x)
Unknown/Not Answered	xxx (xx.x)	xxx (xx.x)	xxx (xx.x)	xxx (xx.x)	xxx (xx.x)
Race, n (%)					
White	xx (xx.x)	xx (xx.x)	xx (xx.x)	xx (xx.x)	xx (xx.x)
Black	xx (xx.x)	xx (xx.x)	xx (xx.x)	xx (xx.x)	xx (xx.x)
Asian	xx (xx.x)	xx (xx.x)	xx (xx.x)	xx (xx.x)	xx (xx.x)
Other	xx (xx.x)	xx (xx.x)	xx (xx.x)	xx (xx.x)	xx (xx.x)
Unknown/Not Answered	xx (xx.x)	xx (xx.x)	xx (xx.x)	xx (xx.x)	xx (xx.x)
Ethnicity, n (%)					
Hispanic or Latino	xx (xx.x)	xx (xx.x)	xx (xx.x)	xx (xx.x)	xx (xx.x)
Not Hispanic or Latino	xx (xx.x)	xx (xx.x)	xx (xx.x)	xx (xx.x)	xx (xx.x)
Unknown/Not Answered	xx (xx.x)	xx (xx.x)	xx (xx.x)	xx (xx.x)	xx (xx.x)
Age (years)					
n	xxx	xxx	xxx	xxx	xxx
Mean	xx.x	xx.x	xx.x	xx.x	xx.x
SD	xx.x	xx.x	xx.x	xx.x	xx.x
Median	xx	xx	xx	xx	xx
Q1, Q3	xx, xx	xx, xx	xx, xx	xx, xx	xx, xx
Min, Max	xx, xx	xx, xx	xx, xx	xx, xx	xx, xx
Age (years), n (%)					
< 60	xx (xx.x)	xx (xx.x)	xx (xx.x)	xx (xx.x)	xx (xx.x)
>=60	xx (xx.x)	xx (xx.x)	xx (xx.x)	xx (xx.x)	xx (xx.x)
Weight (kg)					
N	xxx	xxx	xxx	xxx	xxx
Mean	xx.x	xx.x	xx.x	xx.x	xx.x
SD	xx.x	xx.x	xx.x	xx.x	xx.x
Median	xx	xx	xx	xx	xx
Q1, Q3	xx, xx	xx, xx	xx, xx	xx, xx	xx, xx
Min, Max	xx, xx	xx, xx	xx, xx	xx, xx	xx, xx

Syneos Health #7015085, Chimerix, Inc, Protocol # CMX-DS-004, Post-Cohort 1 or 2 Lock Analysis Shells: Version 2.0, dated 12 Mar 2021

	DSTAT 0.25 N=xxx	Cohort 1 PBO N=xxx	DSTAT 0.325 N=xxx	Cohort 2 PBO N=xxx	Total N=xxx
Height (cm)					
n	xxx	xxx	xxx	xxx	xxx
Mean	xx.x	xx.x	xx.x	xx.x	xx.x
SD	xx.x	xx.x	xx.x	xx.x	xx.x
Median	xx	xx	xx	xx	xx
Q1, Q3	xx, xx	xx, xx	xx, xx	xx, xx	xx, xx
Min, Max	xx, xx	xx, xx	xx, xx	xx, xx	xx, xx
Body mass index (kg/m2)					
n	xxx	xxx	xxx	xxx	xxx
Mean	xx.x	xx.x	xx.x	xx.x	xx.x
SD	xx.x	xx.x	xx.x	xx.x	xx.x
Median	xx	xx	xx	xx	xx
Q1, Q3	xx, xx	xx, xx	xx, xx	xx, xx	xx, xx
Min, Max	xx, xx	xx, xx	xx, xx	xx, xx	xx, xx
Temperature (°C)					
n	xxx	xxx	xxx	xxx	xxx
Mean	xx.x	xx.x	xx.x	xx.x	xx.x
SD	xx.x	xx.x	xx.x	xx.x	xx.x
Median	xx	xx	xx	xx	xx
Q1, Q3	xx, xx	xx, xx	xx, xx	xx, xx	xx, xx
Min, Max	xx, xx	xx, xx	xx, xx	xx, xx	xx, xx
Fever, n(%)					
<= 37.2°C	xx (xx.x)	xx (xx.x)	xx (xx.x)	xx (xx.x)	xx (xx.x)
> 37.2°C to 38.2°C	xx (xx.x)	xx (xx.x)	xx (xx.x)	xx (xx.x)	xx (xx.x)
> 38.2°C	xx (xx.x)	xx (xx.x)	xx (xx.x)	xx (xx.x)	xx (xx.x)
NIAID-Score (IRT), n(%)					
3	xx (xx.x)	xx (xx.x)	xx (xx.x)	xx (xx.x)	xx (xx.x)
4	xx (xx.x)	xx (xx.x)	xx (xx.x)	xx (xx.x)	xx (xx.x)
NIAID-Score (actual), n(%)					
3	xx (xx.x)	xx (xx.x)	xx (xx.x)	xx (xx.x)	xx (xx.x)
4	xx (xx.x)	xx (xx.x)	xx (xx.x)	xx (xx.x)	xx (xx.x)

N = Number of subjects in a specific group; n = Number of subjects with data available; Percentages are based on N;
SD: Standard deviation; Q1, Q3: First, third quartile; Min: minimum; Max: maximum.

Baseline is defined as last measurement prior to or on the date of first study treatment.

NIAID-Score (IRT): directly entered in RAVE by the investigator.

NIAID-Score (actual): calculated using hospitalization and ventilation status at time of randomization.

Page X of Y

This document is confidential.

Page 12 of 45

Table 2: Listing of demographics, baseline characteristics, study drug usage and disposition - Safety Set

Subject Age/Sex	Treatment Group	Race	Ethni- city	Weight (kg)	BMI (kg/m2)	Temp (°C)	NIAID (IRT / actual)	Bolus received / # infusion days		Treatment disposition	Study disposition	Death / Date
999-999 /70/F xx/xx	DSTAT 0.25	Asian	HL	xx.x		xx.x	4 / 4	Yes / 3		Discontinued: AE	Discontinued: Progression	
999-999 xx/xx	Cohort 1 PBO	Other: NHL xxxxxx		xx.x	xx.x		3 / 3	Yes / 7		Discontinued: Other: xxx	Discontinued: FUP	
999-999 xx/xx	Cohort 1 PBO	Other: NHL xxxxxx		xx.x	xx.x		3 / 3	Yes / 7		Completed	Completed	Yes / ddMMYY
999-999 xx/xx	Cohort 1 PBO	Other: NHL xxxxxx		xx.x	xx.x		3 / 4	Yes / 7		Unknown	Ongoing	

Ethnicity: HL=Hispanic or Latino, NHL=Not Hispanic or Latino

NIAID-Score (IRT): directly entered in RAVE by the investigator.

NIAID-Score (actual): calculated using hospitalization and ventilation status at time of randomization.

Page X of Y

(Notes for programmer:

- Sorted by subject number

- Disposition: Progression=Progression of disease, AE=Adverse Event, Prohibited=Patient requires use of a prohibited therapy, Compliance=Non-compliance, FUP=Lost to follow-up, Consent=Patient withdrawal of consent, Physician=Physician decision, Sponsor=Sponsor decision, Improvement=Improvement of condition under study, UNK=Unknown/Not answered)

Table 3: Study drug usage - Safety Set

	DSTAT 0.25 N=xxx	Cohort 1 PBO N=xxx	DSTAT 0.325 N=xxx	Cohort 2 PBO N=xxx
Bolus received, n(%)	xx (xx.x)	xx (xx.x)	xx (xx.x)	xx (xx.x)
Infusion (days received), n(%)				
1	xx (xx.x)	xx (xx.x)	xx (xx.x)	xx (xx.x)
2	xx (xx.x)	xx (xx.x)	xx (xx.x)	xx (xx.x)
3	xx (xx.x)	xx (xx.x)	xx (xx.x)	xx (xx.x)
4	xx (xx.x)	xx (xx.x)	xx (xx.x)	xx (xx.x)
5	xx (xx.x)	xx (xx.x)	xx (xx.x)	xx (xx.x)
6	xx (xx.x)	xx (xx.x)	xx (xx.x)	xx (xx.x)
7	xx (xx.x)	xx (xx.x)	xx (xx.x)	xx (xx.x)

N = Number of subjects in a specific group; n = Number of subjects with data available; Percentages are based on N;
Infusion (days received): Study drug administered at any time during the corresponding study-day (cumulated).

Page X of Y

Table 4: Listing of study drug interruptions / discontinuations - Safety Set

Subject Age/Sex/Race	Treatment Group	Visit	Start Date / Time	Stop Date / Time	Bolus / Infusion no	Total Voulume Given (mL)	Interrupted due to	Permanently discontinued due to
999-999 / 69/F/W	DSTAT 0.25	Baseline (D1)	ddMMMyy hh:mm	ddMMMyy hh:mm	Bolus	999.99	Adverse Event	
		Day 2 (D2)	ddMMMyy hh:mm	ddMMMyy hh:mm	1	999.99		
		Day 3 (D3)	ddMMMyy hh:mm	ddMMMyy hh:mm	2	999.99	Other:xxxxxx	Adverse Event
		Day 4 (D4)	ddMMMyy hh:mm	ddMMMyy hh:mm	3	999.99		Other: xxxxxx
					4	999.99		
999-999 / 35/M/B	Cohort 1 PBO	Baseline (D1)	ddMMMyy hh:mm	ddMMMyy hh:mm	Bolus	999.99	Adverse Event	
			ddMMMyy hh:mm	ddMMMyy hh:mm	1	999.99		
		Day 2 (D2)	ddMMMyy hh:mm	ddMMMyy hh:mm	2	999.99		

Page X of Y

(Note for programmer: Sorted by subject number, start date, start time)

Table 5: Treatment disposition - Safety Set

Treatment disposition	DSTAT 0.25 N=xxx	Cohort 1 PBO N=xxx	DSTAT 0.325 N=xxx	Cohort 2 PBO N=xxx
Primary reason for treatment discontinuation				
Completed treatment, n(%)	xx (xx.x)	xx (xx.x)	xx (xx.x)	xx (xx.x)
Treatment disposition unknown, n(%)	xx (xx.x)	xx (xx.x)	xx (xx.x)	xx (xx.x)
Discontinued treatment, n(%)	xx (xx.x)	xx (xx.x)	xx (xx.x)	xx (xx.x)
Primary reason for treatment discontinuation, n(%)				
Progression of disease	xx (xx.x)	xx (xx.x)	xx (xx.x)	xx (xx.x)
Adverse Event	xx (xx.x)	xx (xx.x)	xx (xx.x)	xx (xx.x)
Patient requires use of a prohibited therapy	xx (xx.x)	xx (xx.x)	xx (xx.x)	xx (xx.x)
Non-compliance	xx (xx.x)	xx (xx.x)	xx (xx.x)	xx (xx.x)
Lost to follow-up	xx (xx.x)	xx (xx.x)	xx (xx.x)	xx (xx.x)
Patient withdrawal of consent	xx (xx.x)	xx (xx.x)	xx (xx.x)	xx (xx.x)
Physician decision	xx (xx.x)	xx (xx.x)	xx (xx.x)	xx (xx.x)
Sponsor decision	xx (xx.x)	xx (xx.x)	xx (xx.x)	xx (xx.x)
Improvement of condition under study	xx (xx.x)	xx (xx.x)	xx (xx.x)	xx (xx.x)
Other	xx (xx.x)	xx (xx.x)	xx (xx.x)	xx (xx.x)
Unknown/Not Answered	xx (xx.x)	xx (xx.x)	xx (xx.x)	xx (xx.x)
Death (during treatment period)	xx (xx.x)	xx (xx.x)	xx (xx.x)	xx (xx.x)

N = Number of subjects in a specific group; n = Number of subjects with data available; Percentages are based on N;

Page X of Y

(Note for programmer: Death (during treatment period) to be derived in case death date = date of last treatment start date or stop date)

Table 6: Study disposition - Randomized Subjects

Study Disposition	DSTAT 0.25 N=xxx	Cohort 1 PBO N=xxx	DSTAT 0.325 N=xxx	Cohort 2 PBO N=xxx
Primary reason for early termination				
Randomized subjects, n (%)	xx (xx.x)	xx (xx.x)	xx (xx.x)	xx (xx.x)
Randomized not treated subjects, n (%)	xx (xx.x)	xx (xx.x)	xx (xx.x)	xx (xx.x)
Treated subjects, n (%)	xx (xx.x)	xx (xx.x)	xx (xx.x)	xx (xx.x)
Completed study, n (%)	xx (xx.x)	xx (xx.x)	xx (xx.x)	xx (xx.x)
Ongoing, n (%)	xx (xx.x)	xx (xx.x)	xx (xx.x)	xx (xx.x)
Discontinued study	xx (xx.x)	xx (xx.x)	xx (xx.x)	xx (xx.x)
Primary reason for study discontinuation, n (%)				
Patient withdrawal of consent	xx (xx.x)	xx (xx.x)	xx (xx.x)	xx (xx.x)
Adverse Event	xx (xx.x)	xx (xx.x)	xx (xx.x)	xx (xx.x)
Use of a prohibited therapy	xx (xx.x)	xx (xx.x)	xx (xx.x)	xx (xx.x)
Non-compliance	xx (xx.x)	xx (xx.x)	xx (xx.x)	xx (xx.x)
Lost to follow-up	xx (xx.x)	xx (xx.x)	xx (xx.x)	xx (xx.x)
Investigator decision	xx (xx.x)	xx (xx.x)	xx (xx.x)	xx (xx.x)
Sponsor decision	xx (xx.x)	xx (xx.x)	xx (xx.x)	xx (xx.x)
Other	xx (xx.x)	xx (xx.x)	xx (xx.x)	xx (xx.x)
Unknown/Not Answered	xx (xx.x)	xx (xx.x)	xx (xx.x)	xx (xx.x)
Death, n (%)	xx (xx.x)	xx (xx.x)	xx (xx.x)	xx (xx.x)

N = Number of randomized subjects in a specific group; n = Number of subjects with data available; Percentages are based on N;

Page X of Y

Table 7: Proportion of subjects who go on invasive mechanical ventilation or ECMO - Safety Set

	DSTAT 0.25 N=xxx	Cohort 1 PBO N=xxx	DSTAT 0.325 N=xxx	Cohort 2 PBO N=xxx
Number of subjects with any invasive mechanical ventilation, ECMO or early study discontinuation, n (%) (a)	xx (xx.x)	xx (xx.x)	xx (xx.x)	xx (xx.x)
Any invasive mechanical ventilation	xx (xx.x)	xx (xx.x)	xx (xx.x)	xx (xx.x)
Early study discontinuation < Day 25	xx (xx.x)	xx (xx.x)	xx (xx.x)	xx (xx.x)
Kaplan-Meier estimates (b)				
Number of censored subjects, n (%) (b)	xx (xx.x)	xx (xx.x)	xx (xx.x)	xx (xx.x)
Time to first invasive mechanical ventilation or ECMO (days) (b)				
25% Quartile (95% CI)	x.x (x.xx,x.xx)	x.x (x.xx,x.xx)	x.x (x.xx,x.xx)	x.x (x.xx,x.xx)
Median (95% CI)	x.x (x.xx,x.xx)	x.x (x.xx,x.xx)	x.x (x.xx,x.xx)	x.x (x.xx,x.xx)
75% Quartile (95% CI)	x.x (x.xx,x.xx)	x.x (x.xx,x.xx)	x.x (x.xx,x.xx)	x.x (x.xx,x.xx)
Number of subjects who stopped invasive mechanical ventilation or ECMO, n(%) (c)	xx (xx.x)	xx (xx.x)	xx (xx.x)	xx (xx.x)
Kaplan-Meier estimates (c)				
Number of censored subjects, n (%) (c)	xx (xx.x)	xx (xx.x)	xx (xx.x)	xx (xx.x)
Duration of first invasive mechanical ventilation or ECMO (days) (c)				
25% Quartile (95% CI)	x.x (x.xx,x.xx)	x.x (x.xx,x.xx)	x.x (x.xx,x.xx)	x.x (x.xx,x.xx)
Median (95% CI)	x.x (x.xx,x.xx)	x.x (x.xx,x.xx)	x.x (x.xx,x.xx)	x.x (x.xx,x.xx)
75% Quartile (95% CI)	x.x (x.xx,x.xx)	x.x (x.xx,x.xx)	x.x (x.xx,x.xx)	x.x (x.xx,x.xx)

N = Number of subjects in a specific group; n = Number of subjects with data available; Percentages are based on N; ECMO: Extracorporeal membrane oxygenation.

(a) Subjects with any invasive mechanical ventilation, ECMO or early study discontinuation before Day 25 will be counted as event.

(b) Kaplan-Meier estimates: Subjects with any invasive mechanical ventilation or ECMO will be counted as event. All other subjects will be censored. Time to first invasive mechanical ventilation or ECMO (days): Days are calculated as (start date/time - first study drug date/time)/24h). Time will be censored at last individual date/time reported. If time is not available for events "00:01" will be imputed, for censored observations "23:59" will be imputed.

(c) Kaplan Meier estimates: Duration of first invasive mechanical ventilation or ECMO (days): Only calculated for subjects with an invasive mechanical ventilation or ECMO reported. Duration is calculated as (stop date/time - start date/time)/24h). If start time is not available "00:01" will be imputed, if end time is missing "23:59" will be imputed. Duration will be censored for subjects with ongoing ventilation at last individual date/time reported.

Page X of Y

Figure 1: Time to first invasive mechanical ventilation or ECMO (KM-Plot) - Safety Set

Kaplan-Meier Plot:

y-axis:

range: 0% to 100% by 20%

label: Event-free Probability

reference-line: 50%

x-axis:

range: 0 to xxx (depending on data), by 7 days

label: Time to Event (Days)

Lines:

solid

different colors/line styles for the treatment-groups

starting at (100%/Baseline)

Censored values marked

Please use the following footnote for Figure 1 :

N = Number of subjects in a specific group; (+) = censored values;

Kaplan-Meier estimates: Subjects with any invasive mechanical ventilation or ECMO will be counted as event. All other subjects will be censored.

Time to first invasive mechanical ventilation or ECMO (days): Days are calculated as (start date/time - first study drug date/time)/24h). Time will be censored at last individual date/time reported. If time is not available for events "00:01" will be imputed, for censored observations "23:59" will be imputed.

Figure 2: Duration of first invasive mechanical ventilation or ECMO (KM-Plot) - Safety Set

Kaplan-Meier Plot:

y-axis:

range: 0% to 100% by 20%
label: Event Probability
reference-line: 50%

x-axis:

range: 0 to xxx (depending on data), by 7 days
label: Duration (Days)

Lines:

solid
different colors/line styles for the treatment-groups
starting at (0%/Baseline)
Censored values marked

Please use the following footnote for Figure 2 :

N = Number of subjects in a specific group; (+) = censored values;

Kaplan Meier estimates: Duration of first invasive mechanical ventilation or ECMO (days): Only calculated for subjects with an invasive mechanical ventilation or ECMO reported. Duration is calculated as (stop date/time - start date/time)/24h. If start time is not available "00:01" will be imputed, if end time is missing, "23:59" will be imputed. Duration will be censored for subjects with ongoing ventilation at last individual date/time reported.

Table 8: Treatment-emergent Adverse Events (TEAEs) - Safety Set

Primary system organ class Preferred term	DSTAT 0.25 N=xxx n (%)	Cohort 1 PBO N=xxx n (%)	DSTAT 0.325 N=xxx n (%)	Cohort 2 PBO N=xxx n (%)
Number (%) of subjects with at least one such AE	xx (xx.x)	xx (xx.x)	xx (xx.x)	xx (xx.x)
SOC 1	xx (xx.x)	xx (xx.x)	xx (xx.x)	xx (xx.x)
PT 1	xx (xx.x)	xx (xx.x)	xx (xx.x)	xx (xx.x)
PT 2	xx (xx.x)	xx (xx.x)	xx (xx.x)	xx (xx.x)
:	xx (xx.x)	xx (xx.x)	xx (xx.x)	xx (xx.x)
SOC 2	xx (xx.x)	xx (xx.x)	xx (xx.x)	xx (xx.x)
:	xx (xx.x)	xx (xx.x)	xx (xx.x)	xx (xx.x)

N = Number of subjects in a specific group; n = Number of subjects with at least one event in the category;

Percentages are based on N; Adverse events are coded using MedDRA version 23.0.

If a subject has multiple occurrences of an AE, the subject is presented only once in the respective subject count (n).

Page X of Y

(Note for programmer: AEs are sorted by descending patients' frequency of SOC and by descending frequency of PT within the SOC in the DSTAT 0.25)

Table 9: Severe, life-threatening or fatal treatment emergent Adverse Events - Safety Set

For the layout refer to Table 8

(Notes for programmer:

- Change first line in the table to "Number (%) of subjects with at least one such AE".
- TEAEs with the following AE severity grades are reported: Grade 3 (Severe), Grade 4 (Life-threatening), Grade 5 (Fatal)..)

Table 10: Treatment emergent Adverse Events leading to study drug discontinuation - Safety Set

For the layout refer to Table 8

(Note for programmer: Change first line in the table to "Number (%) of subjects with at least one such AE".

Table 11: Serious treatment emergent Adverse Events - Safety Set

For the layout refer to Table 8

(Note for programmer: Change first line in the table to "Number (%) of subjects with at least one such TEAE".

Table 12: Listing of Serious Adverse Events and Adverse Events of Special Interest - Safety Set

Subject Age/Sex/Race	Treatment Group	Preferred term Verbatim	Start Date (Study Day)	Stop Date (Study Day)	Severity	Relationship	Serious AE	AE of Special Interest	Action taken with study drug	
999-999 / 70/F/W	DSTAT 0.25	PT1xxxxxxxx	DdMMMyy (xx)	DdMMMyy (xx)	Mild	Related	Fatal	Yes	Yes	Discontinued
999-999 / xx/xx/xx	Cohort 1 PBO	PT1xxxxxxxx	DdMMMyy (xx)	DdMMMyy (xx)	Mild	Related	Recovered	No	Yes	No Change

Note: Adverse events are coded using MedDRA version 23.0.

Study Days prior to first treatment date are calculated as (actual date - first treatment date), after first treatment date as (actual date - first treatment date) + 1.

Page 1 of x

(Notes for programmer:

- Sorted by subject number, start date, stop date, Preferred term and Verbatim
- Outcome: Ongoing=Not recovered (Ongoing), Sequelae=Recovered with Sequelae, Unknown=Unknown/Lost to Follow-up
- Action taken with study drug: Interrupted=Study drug temporarily interrupted, Discontinued=Study drug permanently discontinued

Table 13: Overview CTCAE v5.0 Grades

Parameter	Grade 1	Grade 2	Grade 3	Grade 4
Hemoglobin	<LLN - 10.0 g/dL <LLN - 6.2 mmol/L <LLN - 100 g/L	<10.0 - 8.0 g/dL <6.2 - 4.9 mmol/L <100 - 80g/L	<8.0 g/dL <4.9 mmol/L <80 g/L	NA
Platelets		<LLN - 75,000/mm ³ ; <LLN - 75.0 x 10 ⁹ /L	<75,000 - 50,000/mm ³ ; <75.0 - 50.0 x 10 ⁹ /L	<50,000 - 25,000/mm ³ ; <50.0 - 25.0 x 10 ⁹ /L
Activated Partial Thromboplasting Time (aPTT)	>ULN - 1.5 x ULN	>1.5 - 2.5 x ULN	>2.5 x ULN	NA
Prothrombin Intl. Normalized Ratio (INR)	>1.2 - 1.5	>1.5 - 2.5	>2.5	NA
Aspartate Aminotransferase (AST)	>ULN - 3.0 x ULN	>3.0 - 5.0 x ULN	>5.0 - 20.0 x ULN	>20.0 x ULN
Alanine Aminotransferase (ALT)	>ULN - 3.0 x ULN	>3.0 - 5.0 x ULN	>5.0 - 20.0 x ULN	>20.0 x ULN
Total Bilirubin	>ULN - 1.5 x ULN	>1.5 - 3.0 x ULN	>3.0 - 10.0 x ULN	>10.0 x ULN
Creatinine	>ULN - 1.5 x ULN	>1.5 - 3.0 x ULN	>3.0 - 6.0 x ULN	>6.0 x ULN
Creatinine Clearance, Estimated	<LLN - 60 ml/min	<60 - 30 ml/min	<30 - 15 ml/min	<15 ml/min

NA = Not applicable, ULN = Upper limit of normal, LLN = Lower limit of normal.

Grade 0 : Any result not graded 1, 2, 3, 4 or Unknown.

Grade Unknown : Missing result or missing upper limit of normal for parameters requiring ULN for grading.

(Notes for programmer:

- LLN for creatinine clearance is fixed 90 mL/min
- Calculation of creatinine clearance (CC) (Cockcroft-Gault):

$$(140 - \text{age (years)})$$

$$CC \text{ (ml/min)} = \frac{140 - \text{age (years)}}{0.8143 \times \text{serum creatinine (}\mu\text{mol/L)}} \times \text{baseline weight (kg)} \times (0.85 \text{ if female})$$

)

Table 14: Distribution of laboratory grade by parameter and visit - Safety Set

Parameter: <Hemoglobin> <Platelets> <Activated partial thromboplastin time (aPTT)> <Prothrombin International Normalized Ratio (INR)> <Aspartate aminotransferase (AST)> <Alanine aminotransferase (ALT)> <Total bilirubin> <Creatinine> <Creatinine Clearance, Estimated >

Scheduled Visit Grades (a)	DSTAT 0.25 N=xxx	Cohort 1 PBO N=xxx	DSTAT 0.325 N=xxx	Cohort 2 PBO N=xxx
Baseline				
Grade 0	xx (xx.x)	xx (xx.x)	xx (xx.x)	xx (xx.x)
Grade 1	xx (xx.x)	xx (xx.x)	xx (xx.x)	xx (xx.x)
Grade 2	xx (xx.x)	xx (xx.x)	xx (xx.x)	xx (xx.x)
Grade 3	xx (xx.x)	xx (xx.x)	xx (xx.x)	xx (xx.x)
Grade 4	xx (xx.x)	xx (xx.x)	xx (xx.x)	xx (xx.x)
Unknown	xx (xx.x)	xx (xx.x)	xx (xx.x)	xx (xx.x)
Maximum Post-baseline Grade				
Grade 0	xx (xx.x)	xx (xx.x)	xx (xx.x)	xx (xx.x)
Grade 1	xx (xx.x)	xx (xx.x)	xx (xx.x)	xx (xx.x)
Grade 2	xx (xx.x)	xx (xx.x)	xx (xx.x)	xx (xx.x)
Grade 3	xx (xx.x)	xx (xx.x)	xx (xx.x)	xx (xx.x)
Grade 4	xx (xx.x)	xx (xx.x)	xx (xx.x)	xx (xx.x)
Unknown	xx (xx.x)	xx (xx.x)	xx (xx.x)	xx (xx.x)

N = Number of subjects in a specific group; n = Number of subjects with data available; Percentages are based on N; (a) CTCAE v5.0 grades using absolute thresholds without accounting for baseline.

Baseline value is defined as the last non-missing measurement prior to, or on the date/time of the first administration of study treatment.

NA = not applicable

Page X of Y

(Notes for programmer:

- CTCAE Grades: Unknown: missing result (or missing upper limit of normal for parameters requiring ULN for grading). Grade 0: any result not graded 1, 2, 3, 4 or Unknown.
- display only for visit Baseline and Maximum Grade per subject and all 6 categories (Grade 0 - Grade 4 and Unknown), if applicable.
- generate a post-baseline Maximum Grade per subject (incl. unscheduled measurements)
- for the generation of Maximum Grade use the following order: Unknown - Grade 0 - Grade 1, ..., Grade 4)
- Calculation of creatinine clearance (CC) (Cockcroft-Gault):
(140 - age (years))

CC (ml/min) = ----- * baseline weight (kg) * (0.85 if female)
0.8143 * serum creatinine (μmol/L)

)

Table 15: Listing of laboratory results - Safety Set

Subject Age/Sex/Race	Treatment Group	Parameter	Date/Time	Visit	Value \$	Unit	Lower Limit	Upper Limit	Grade (a)	
999-999 70/F/W	DSTAT 0.25	Hemoglobin	Ddmmmyy/mm:hh	Screening	99999 H	NCS	Unit	LLL	UUU	1
			Ddmmmyy/mm:hh	Baseline	99999 L	CS	Unit	LLL	UUU	4

(a) CTCAE v5.0 grades using absolute thresholds without accounting for baseline. Grade=0 and Grade=Unknown are not displayed.
\$: H = Above upper limit of normal; L = Below lower limit of normal, NCS = Not clinically significant, CS= Clinically significant.
Visit "Early Tx DC (TXDC)" denotes Early Treatment Discontinuation Visit.

(Notes for programmer:

- Sorted by subject number, Parameter, date and time
- The following parameter will be displayed: Hemoglobin, platelets, activated partial thromboplastin time (aPTT), prothrombin time (PT), prothrombin international normal ratio (INR), d-dimer, Anti-Xa, aspartate aminotransferase (AST), alanine aminotransferase (ALT), total bilirubin, creatinine, Creatinine Clearance, Estimated.
- LLN for creatinine clearance is fixed 90 mL/min
- CTCAE Grades: reference Table 13.)

Table 16: Shift-table of laboratory results - Safety Set

Parameter: <Hemoglobin> <Platelets> <Activated partial thromboplastin time (aPTT)> <prothrombin time (PT)> <Prothrombin International Normalized Ratio (INR)> <d-dimer> <Anti-Xa> <Aspartate aminotransferase (AST)> <Alanine aminotransferase (ALT)> <Total bilirubin> <Creatinine> <Creatinine Clearance, Estimated>

DSTAT 0.25 N=xxx				Cohort 1 PBO N=xxx				Baseline (D1)				DSTAT 0.325 N=xxx				Cohort 2 PBO N=xxx																										
<LLN			Normal	>ULN			<LLN			Normal	>ULN			<LLN			Normal	>ULN			<LLN			Normal	>ULN																	
Post-Baseline																																										
